	measure (instrument, scale, source)	
Young person: SDQ, carer-report version; Child conviction or subject to youth caution (SSDA903 2023-2024); transition into residential care (SSDA903 2023-2024); unplanned moves (SSDA903 2023-2024); missing from care episodes (SSDA903 2023-2024)
 
SSW / YPSW: ARTIC Scale prior to randomisation
 
FCs: Professional Quality of Life Scale (self-report); bespoke questionnaire (self-report) as close as possible to randomisation of YPSW

Randomisation

There are constraints on the number of training places per LA⁴, so YPSWs per LA have not typically been allocated to intervention and control group in the ratio 50:50. Instead, the percentage allocated to the intervention was set so that all available places were filled, with up to a maximum of 70% being allocated to the intervention. In practice, for most LAs, the percentage allocated to the intervention was around 46%. Randomisation was run separately per LA by the trial statistician, giving implicit stratification by LA. Since the trial statistician is undertaking the randomisation and will conduct the statistical analysis, the analysis will not be blind to allocation.

A significant complication in this trial is that the primary analysis aims to test whether delivering the intervention to both SSWs and YPSWs improves outcomes for YP, rather than simply testing whether delivering the intervention to one set of professionals or the other has an impact. Yet, SSWs do not cluster within YPSWs (or vice versa), so straightforward randomisation of YPSW/SSW pairs is not feasible. Inevitably some young people in each LA will have a SSW who has been assigned to the intervention group and a YPSW who has been assigned to the control group, and vice versa. That is, when the randomisation is complete, there will be YP in each of four arms, with the first two (in bold) being the primary analysis arms:

⁴ Depending on the number of in-scope social workers in an LA, either one or two training groups were allocated to the LA, with the maximum number of places per group being 35.

Arm 1: T_{SSW}T_{YPSW} (i.e. both SSW and YPSW assigned to the intervention);

Arm 2: C_{SSW}C_{YPSW} (i.e. both SSW and YPSW assigned to the control group);

Arm 3: T_{SSW}C_{YPSW} (i.e. SSW assigned to the intervention and YPSW assigned to the control group);

Arm 4: C_{SSW}T_{YPSW} (i.e. SSW assigned to the control group and YPSW assigned to the intervention group).

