This approach to randomisation does not give a four-arm RCT with balance across all four arms. Analysis Arms 1 and 2 will be balanced (which is vital for the primary analysis), and Arms 3 and 4 will be balanced, but the YP in Arms 3 and 4 will have different experiences to those in Arms 1 and 2 in the sense that the Arms 3 and 4 YP will be more likely to have a YPSW and SSW who work together infrequently. This does not affect the primary analysis, which compares just Arms 1 and 2, but in the exploratory analysis that compares all four arms the lack of balance will be acknowledged.

Once randomisation has been completed, each young person will have been assigned to one of the four randomisation arms. Some contamination during the trial is inevitable (with some 'control' YP being assigned to a trained social worker during the trial and vice versa). This will be monitored and sensitivity analysis will be conducted to establish the degree to which this dilutes the overall effect sizes (see analysis section).

Sample size calculations overview

Our primary analysis (which uses externalising behaviour as measured through the SDQ as an outcome) focuses on the YP where both the YPSW and SSW have either been assigned to the intervention group or to the control group (Analysis Arms 1 and 2 as described in the randomisation section above). Arms 1 and 2 between them cover 66% of all the eligible YP identified as in-scope for the trial.

Table 2 sets out the MDES and sample sizes that were originally anticipated and as they were presented in version 1 of the trial protocol. The final column sets out our revised estimates after recruitment of LAs, baseline data collection, and randomisation. The original intention was to recruit 10 LAs to the trial rather than the eight achieved, and the initial predictions of response rate at baseline proved too optimistic. However, the number of social workers was much larger than anticipated, which reduces the average cluster size. Nevertheless, the MDES

has increased from the initial protocol estimate of 0.21 standard deviations to 0.24 standard deviations.

The assumptions behind the calculations are:

- Across the eight LAs, the total number of eligible YP is 1,477. Of these, 979 have been assigned to one of the two primary analysis arms: 458 to the group where both the YPSW and the SSW are assigned to the intervention group and 521 to the group where both the YPSW and the SSW are assigned to the control group.

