where

n_1 is the achieved sample size in the intervention arm (Group 1);

n_2 is the achieved sample size in the control arm (Group 2);

m is the average cluster size;

ρ is the ICC; and

R is the correlation between the baseline and follow-up score.

The value 1.96 is the z-value for a type 1 error rate (alpha) of 0.05, and 0.84 is the z-value for 80% power.

Table 2 sets out the assumptions for the primary outcome (externalising SDQ score). The assumptions do not all hold for the secondary outcomes, the major differences being:

- For SSDA903 outcomes which are collected via administrative systems, the sample sizes will be somewhat larger because losses to the sample will be lower. The correlation between baseline and follow-up is not known but is likely to be low for the non-SDQ scores at least, and the ICC is not known, but overall we expect an MDES of around 0.20sd for these outcomes;
- There will be fewer FCs than YP in the analysis as FCs may care for more than one eligible YP, our best current assumption being that it will be around 139 in Group 1 and 163 in Group 2. We estimate an MDES of 0.27sd for their outcomes.
- There are 422 YPSWs and 264 SSWs in the trial (686 overall), divided into two groups, intervention and control, with around 316 in the intervention arm and 370 in the control arm per arm (139 and 163 respectively after non-response). For their outcomes we estimate an MDES of around 0.23sd.

Table 2: Sample size calculations

	Protocol version 1	Post randomisation
Minimum Detectable Effect Size (MDES)	0.21 sd	0.24 sd

		Protocol version 1	Post randomisation
Pre-test/ post-test correlations	level 1 (participant)	0.6	0.6
	level 2 (cluster)	0	0
Intracluster correlations (ICCs)	level 1 (participant)	0	0
	level 2 (cluster)	0.2	0.2
Alpha ⁷		0.05	0.05
Power		0.8	0.8
One-sided or two-sided?		Two	Two
Average cluster size		7.7	1.5
Number of clusters ⁸	intervention	70 YPSWs	198 YPSWs/124 SSWs at randomisation stage
	control	70 YPSWs	224 YPSWs/140 SSWs at randomisation stage
	total	140 YPSWs	422 YPSWs/264 SSWs
Number of participants	intervention	540	183 (after non-response)
	control	540	208 (after non-response)
	total	1,080	391

⁷ Please adjust as necessary for trials with multiple primary outcomes, 3-arm trials etc. when a Bonferroni correction is used to account for family-wise errors.

⁸ Please adjust as necessary e.g., for trials that are randomised at the setting, practitioner or participant level.

Analysis

Primary outcome analysis

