An exploratory analysis for the primary and secondary outcomes will include Analysis Arms 3 and 4 in the regression model, that is the groups of YP where one social worker (YPSW or SSW) was randomised to training and the other to control. For this analysis the trial will be assumed to follow a factorial design. The regressions for this analysis will generate three effect estimates: the effect of the intervention being delivered to SSWs; the effect of the intervention being delivered to YPSWs; and the additive effect of the intervention being delivered jointly to SSWs and YPSWs (that is, the interaction effect). Differences between the effect sizes will be tested for significance, but given the relatively small sample sizes in Arms 3 and 4 we do not anticipate they will reach significance, so the results will be presented purely descriptively. Given that Arms 3 and 4 are not balanced with Arms 1 and 2 (see randomisation section), this analysis will be presented with suitable caveats, and the fact that the effect sizes may be biased, will be explained.

The model for this analysis is:

$$Y_{ijk} = \beta_0 + \beta_1 Z_{1ik} + \beta_2 Z_{2ik} + \beta_3 Z_{1ik} Z_{2ik} + \beta_4 X_{ijk} + \beta_5 LA_k + u_{ijk} + \varepsilon_{ijk} \quad (\text{Eq 4})$$

where

Y_{ijk} = outcome score at follow-up for young person i assigned at baseline to YPSW j within LA k;

$\beta_0, \beta_1, \beta_2, \beta_3, \beta_4, \beta_5$ = fixed effect parameters;

Z_{1ik} = indicator variable for allocation of the YP's YPSW (0=control; 1=intervention) within LA k;

Z_{2ik} = indicator variable for allocation of the YP's SSW (0=control; 1=intervention) within LA k;

X_{ijk} = baseline externalising score for young person i assigned at baseline to YPSW j within LA k;

LA_k = a vector for the local authority dummy variables, of which there will be seven. β_3 is a coefficient vector for the LA dummy covariates;

u_{ij} = random effect for ith member of YPSW j;

ε_{ijk} = residual error term for ith member of cluster j.

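### Arms 1 and 2 are not exactly balanced on SSW–YPSW tie status (a small effect on Eq 1); Eq 4 confounds that status with all three of its effects, and a variable fixed before randomisation could remove this

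*SAP*

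**What the plan says.** The Randomisation section of the SAP links each SSW, before allocation, to the one YPSW with whom they share most eligible YP (Step 1). YPSWs are then randomised within LA (Step 2), and each SSW takes the allocation of the linked YPSW (Step 3). The section states that "YPSWs per LA have not typically been allocated to intervention and control group in the ratio 50:50". Places were filled "with up to a maximum of 70% being allocated to the intervention", and "In practice, for most LAs, the percentage allocated to the intervention was around 46" per cent. Table 2 gives "198 YPSWs/124 SSWs at randomisation stage" in the intervention group, out of 422 YPSWs in all.

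On comparability it says "Analysis Arms 1 and 2 will be balanced (which is vital for the primary analysis". It accepts that YP in Arms 3 and 4 differ, because their two workers tend to work together less often, and adds: "This does not affect the primary analysis, which compares just Arms 1 and 2".

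Eq 1 adjusts for the baseline score and LA. Eq 4 adds Arms 3 and 4 as a factorial design with the same adjustment. It opens its caveat with "Given that Arms 3 and 4 are not balanced with Arms 1 and 2" and warns that effect sizes may be biased. Its third effect is described as "the additive effect of the intervention being delivered jointly to SSWs and YPSWs (that is, the interaction effect".

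**The concern.** Whether a YP is tied determines their chance of landing in each arm. A tied YP can only be in Arm 1 or 2. An untied YP can be in any of the four, and reaches Arm 1 or Arm 2 only when two separate YPSW allocations agree. Unless allocation is 50:50, this changes the tied/untied mix between Arms 1 and 2. It does so within each LA, so the LA dummies in Eq 1 do not remove it. Tie status is also related to how often the two workers work together, the feature the SAP itself gives as the reason the arm pairs differ.

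Two things are at stake. A property on which the SAP rests its primary comparison is stated more strongly than the design delivers. And the four-arm analysis could report a tied/untied difference as an effect of training one worker, or as an interaction, although the variable needed to separate them exists before randomisation.

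**Working it through.** **Inputs from the SAP.** 1,477 eligible YP, 979 in Arms 1 and 2 (458 and 521); 198 of 422 YPSWs in intervention, 46.9%; about 46% in most LAs; cap 70%; analysed n 183 and 208; cluster size 1.5; ICC 0.2; R 0.6.

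**Not in the SAP.** The tied fraction t is inferred below. The tied-minus-untied follow-up difference d is assumed, with a range of 0.1 to 0.5 sd.

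1. *The SAP's own figure.* MDES = 2.8 × sqrt[(1/183 + 1/208) × 1.1 × 0.64] = 0.238, as stated (0.24).

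2. *Arm probabilities at allocation p.* Tied: Arm 1 p, Arm 2 1-p, Arms 3 and 4 zero. Untied: Arm 1 about p², Arm 2 about (1-p)², Arms 3 and 4 about p(1-p) each. So Arms 3 and 4 do balance with each other.

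3. *Tied fraction.* Solve t + (1-t)(p² + (1-p)²) = 979/1,477 = 0.663. At p = 0.469 the bracket p² + (1-p)² is 0.502, so t = (0.663 - 0.502)/(1 - 0.502) = 0.32.

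4. *Tied share by arm.* Arm 1: t/(t + (1-t)p). Arm 2: t/(t + (1-t)(1-p)).

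| p | Arm 1 | Arm 2 | Difference (points) |
|---|---|---|---|
| 0.46 | 50.9% | 46.9% | +4.0 |
| 0.469 | 50.4% | 47.3% | +3.1 |
| 0.50 | 48.8% | 48.8% | 0 |
| 0.70 | 40.5% | 61.4% | -20.9 |

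With t anywhere from 0.2 to 0.5, the difference at p = 0.46 stays between 3.6 and 4.0 points. Simulating the randomisation steps with fixed-count allocation and assumed sharing patterns gives 4.4 to 4.9 points.

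5. *Eq 1 bias* = difference × d. At p = 0.46: 0.040 × 0.1 = 0.004 sd; 0.040 × 0.3 = 0.012 sd; 0.040 × 0.5 = 0.020 sd. If d is equally present at baseline, adjustment at R = 0.6 leaves about (1 - 0.6)d = 0.4d, so at d = 0.3 the bias is about 0.005 sd.

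6. *Eq 4 bias.* The four arms have tied shares 0.509, 0.469, 0 and 0 (p = 0.46). Each single-worker effect compares Arm 3 or Arm 4 with Arm 2: 0 - 0.469 = -0.469d. The interaction is Arm 1 - Arm 3 - Arm 4 + Arm 2: 0.509 + 0.469 = +0.978d. At p = 0.50 these are -0.488d, -0.488d and +0.977d, so equal allocation does not help. At d = 0.3 the interaction bias is 0.29 sd if d is absent at baseline, and about 0.978 × 0.4 × 0.3 = 0.12 sd if it is fully present there.

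7. *The joint effect.* The sum beta1 + beta2 + beta3 is the Arm 1 minus Arm 2 contrast. Its bias is -0.469 - 0.469 + 0.978 = +0.040d, the same small figure as Eq 1. Under 0/1 coding, beta3 alone is the departure from additivity.

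8. *The remedy.* In simulation, adding a tied indicator takes the Eq 1 bias to 0.000. In Eq 4 it takes all three biases to zero only if the training effect is the same in tied and untied YP. If a joint effect exists only in tied YP, the additive indicator leaves about 0.17 to 0.20 of it in each single-worker coefficient and 0.08 to 0.09 in the interaction. Fitting Eq 4 in untied YP gives 0, 0 and 0, the true values for them.

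9. *Appendix example.* Recounting gives 11/20/3/12, as stated. Nineteen of the 46 YP are tied: 6 in Arm 1, 13 in Arm 2, none in Arms 3 or 4.

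**The case against.** **On size.** At the realised allocation the primary bias is about 0.01 sd against an MDES of 0.24. A reader might take the 21-point gap at p = 0.70 (0.209 × 0.3 = 0.06 sd) as the state of this trial. The SAP does not support that: 70% is a ceiling, and no LA is said to have reached it. If the other LAs were at 46%, an overall 46.9% leaves room for about (46.9 - 46)/(70 - 46) = 4% of YPSWs at 70%, and the imbalance there has the opposite sign. The observed Arm 1 share, 458/979 = 46.8%, is close to the 45.3% the calculation predicts, a gap of about one standard error (0.016, ignoring clustering). It neither confirms nor refutes the mechanism. This objection stands in full for Eq 1.

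**On Eq 4.** The SAP discloses the imbalance, calls the analysis exploratory and presents it descriptively. That stands too; the remaining point is that a caveat is offered where an adjustment is available. A reader might also call an interaction bias near 0.3 sd larger than the MDES. That is the wrong benchmark, because 0.24 belongs to the two-arm contrast. With the same response in Arms 3 and 4 (498 × 0.57 × 0.70 = 199, about 99 each), the SAP's formula gives about 0.41 sd for the interaction.

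**On tie status as a marker.** Step 1 ties are broken at random, and in the Appendix four of the ten SSWs share one YP with each of their YPSWs. Being tied is therefore only a proxy for close working, which makes a large d less likely. It does not alter the arm probabilities, which depend on tie status itself.

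**On the interaction wording.** Eq 4 is a standard form and the SAP does name the term an interaction. Only its description as the additive effect of joint delivery misleads.

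**Conclusion.** The statement that Arms 1 and 2 will be balanced is not exact. Within LA the tied share differs by about 3 to 5 points at the realised allocation, and Eq 1 carries a bias of about 0.005 to 0.02 sd for d of 0.1 to 0.5 sd, less if the baseline score already reflects d. A reader might infer that the primary result is compromised; the SAP's own figures do not support that.

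The larger defect is in Eq 4. Any d not captured by the baseline score enters the single-worker effects at about -0.47d each and the interaction at about +0.98d, even near 50:50. It would also be too strong to say that one added indicator repairs both models. For Eq 4 that is true only if the training effect does not depend on tie status.

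The structure follows from the SAP's randomisation steps. The sizes rest on t = 0.32, which is inferred, and on d, for which the SAP gives no value.

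**What to change.** - In the Randomisation section, say that Arms 1 and 2 are balanced within LA and tie status, and only approximately overall when allocation is not 50:50.
- Derive a tied indicator from the Step 1 list, which the trial statistician already holds, and add it to the baseline characteristics table, which does not list it.
- Add the indicator to Eq 1, with LA-by-tied terms if its effect varies by LA, or at least report this as a sensitivity analysis.
- Fit Eq 4 in untied YP only, or in all YP with the tied indicator and a tied-by-group term. In the second form beta1, beta2 and beta3 describe untied YP, and the tied-by-group coefficient is added to their sum to give the joint effect in tied YP.
- Describe beta3 as the interaction, that is, the departure from additivity, and report beta1 + beta2 + beta3 as the joint effect.

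The cost is SAP wording and at most eight degrees of freedom in Eq 1 (one indicator and seven LA terms); with the single indicator the MDES stays at 0.24. Restricting Eq 4 to untied YP lowers precision and narrows the population to which its results apply.

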where

n_1 is the achieved sample size in the intervention arm (Group 1);

n_2 is the achieved sample size in the control arm (Group 2);

m is the average cluster size;

ρ is the ICC; and

R is the correlation between the baseline and follow-up score.

The value 1.96 is the z-value for a type 1 error rate (alpha) of 0.05, and 0.84 is the z-value for 80% power.

Table 2 sets out the assumptions for the primary outcome (externalising SDQ score). The assumptions do not all hold for the secondary outcomes, the major differences being:

- For SSDA903 outcomes which are collected via administrative systems, the sample sizes will be somewhat larger because losses to the sample will be lower. The correlation between baseline and follow-up is not known but is likely to be low for the non-SDQ scores at least, and the ICC is not known, but overall we expect an MDES of around 0.20sd for these outcomes;
- There will be fewer FCs than YP in the analysis as FCs may care for more than one eligible YP, our best current assumption being that it will be around 139 in Group 1 and 163 in Group 2. We estimate an MDES of 0.27sd for their outcomes.
- There are 422 YPSWs and 264 SSWs in the trial (686 overall), divided into two groups, intervention and control, with around 316 in the intervention arm and 370 in the control arm per arm (139 and 163 respectively after non-response). For their outcomes we estimate an MDES of around 0.23sd.

Table 2: Sample size calculations

	Protocol version 1	Post randomisation
Minimum Detectable Effect Size (MDES)	0.21 sd	0.24 sd

		Protocol version 1	Post randomisation
Pre-test/ post-test correlations	level 1 (participant)	0.6	0.6
	level 2 (cluster)	0	0
Intracluster correlations (ICCs)	level 1 (participant)	0	0
	level 2 (cluster)	0.2	0.2
Alpha ⁷		0.05	0.05
Power		0.8	0.8
One-sided or two-sided?		Two	Two
Average cluster size		7.7	1.5
Number of clusters ⁸	intervention	70 YPSWs	198 YPSWs/124 SSWs at randomisation stage
	control	70 YPSWs	224 YPSWs/140 SSWs at randomisation stage
	total	140 YPSWs	422 YPSWs/264 SSWs
Number of participants	intervention	540	183 (after non-response)
	control	540	208 (after non-response)
	total	1,080	391

⁷ Please adjust as necessary for trials with multiple primary outcomes, 3-arm trials etc. when a Bonferroni correction is used to account for family-wise errors.

⁸ Please adjust as necessary e.g., for trials that are randomised at the setting, practitioner or participant level.

Analysis

Primary outcome analysis

The analysis of the efficacy trial data will be on an intention-to-treat basis. Estimates of impact per outcome will be based on a multilevel linear regression model with two levels, YPSW and YP, with the baseline version of each outcome being entered as a covariate. LA will be entered as a fixed effect. The analysis will be conducted in SPSS v28.0.1.1 via the MIXED procedure.

If, after non-response, we have data that is essentially unclustered then a single-level model will be fitted.

Primary outcome analysis

The primary outcome measure for YP in the trial is the SDQ externalising score.

The SDQ questionnaire includes five subscales, each with five items, that measure: 1. Emotional symptoms; 2. Conduct problems; 3. Hyperactivity/inattention; 4. Peer problems; 5. Prosocial behaviour. FCs score from 0 to 2 on each item using a scale 'not true', 'somewhat true' or 'certainly true', thus producing a score for each subscale from 0 to 10, where a lower total score is a better outcome for subscales 1-4, and the reverse for subscale 5 (prosocial behaviour). The 'externalising' score (from 0 to 20), is generated by summing the scores of the conduct and hyperactivity subscales.

The calculation of the externalising score will follow the standard SDQ scoring rules. The score will only be calculated where both subscales have a valid score (that is, at least three of the five items have been answered), others being set to missing. Each subscale will be calculated as (total subscale score)*5/(number answered).

The main regression model specification is as follows:

$$Y_{ijk} = \beta_0 + \beta_1 \text{Group}_{jk} + \beta_2 X_{ijk} + \beta_3 LA_k + u_{ijk} + \varepsilon_{ijk} \quad (\text{Eq 1})$$

where

Y_{ijk} = externalising score at follow-up for young person i belonging to assigned at baseline to YPSW j within LA k;

$\beta_0, \beta_1, \beta_2, \beta_3$ = fixed effect parameters;

Group_{jk} = indicator variable for group allocation of the YP's YPSW and SSW (0=control; 1=intervention) within LA k;

X_{ijk} = baseline externalising score for young person i assigned at baseline to YPSW j within LA k;

LA_k = a vector for the local authority dummy variables, of which there will be seven. β_3 is a coefficient vector for the LA dummy covariates;

u_{ij} =random effect for i th member of YPSW j ;

ε_{ijk} = residual error term for i th member of cluster j .

If, at the analysis stage, the average cluster size proves to be very close to one (that is 1.1 or below) we will use a single-level model rather than two-level. In this case the model will be:

$$Y_{ik} = \beta_0 + \beta_1 Group_{ik} + \beta_2 X_{ik} + \beta_3 LA_k + \varepsilon_{ik} \quad (\text{Eq 2})$$

where

Y_{ik} =externalising score at follow-up for young person i within LA k ;

$\beta_0, \beta_1, \beta_2, \beta_3$ = fixed effect parameters;

$Group_{ik}$ = indicator variable for group allocation of the YP's YPSW and SSW (0=control; 1=intervention) within LA k ;

X_{ik} = baseline externalising score for young person i within LA k ;

LA_k = a vector for the local authority dummy variables, of which there will be seven. β_3 is a coefficient vector for the LA dummy covariates;

ε_{ik} = residual error term.

Secondary outcome analysis

There are a range of secondary outcome measures reflecting the fact that the Theory of Change suggests that impacts should be observed for all the groups potentially affected by the SW training, namely YP, FCs, and the social workers themselves.

1. Young people

There are six secondary outcomes for YP:

- The SDQ internalising score (continuous variable);
- The SDQ prosocial score (continuous variable);

and four outcomes taken from SSSA903 data:

- One or more unplanned moves (binary);

- Transition into residential care (binary);
- Conviction or subject to youth caution (binary);
- Any missing from care episodes (binary).

2. Foster carers

There are four secondary outcomes for foster carers (detailed in the trial protocol):

- The three Professional Quality of Life (ProQOL) subscales (continuous variables):
 - o compassion satisfaction;
 - o burnout;
 - o secondary traumatic stress.
- Knowledge and understanding of TIP score (continuous).

3. Social workers

For social workers in the trial, there is just one secondary outcome:

- ARTIC score (continuous)

The analysis of the secondary outcomes will be conducted following similar overall model specifications as the primary outcome analysis, but with some modifications to reflect the nature of the data. These are:

- The models for the binary outcomes will be logistic regressions rather than linear;
- For the SSDA903 outcomes, for YP just entering foster care there will be no applicable baseline data. To account for this, a baseline outcome will be included in the model coded as categorical: present, absent; not applicable.
- The regression model for social worker outcomes will be specified using the primary outcome model, but there will be no clustering effects for YPSWs given that these are the units of randomisation. Here the model will be:

$$Y_{jk} = \beta_0 + \beta_1 Group_{jk} + \beta_2 X_{jk} + \beta_3 LA_k + \varepsilon_{jk} \quad (\text{Eq 3})$$

where

Y_{jk} = ARTIC score at follow-up for SW j within LA k;

$\beta_0, \beta_1, \beta_2, \beta_3$ = fixed effect parameters;

$Group_{jk}$ = indicator variable for group allocation (0=control; 1=intervention) within LA k;

X_{jk} = baseline ARTIC score for SWj within LA k;

LA_k = a vector for the local authority dummy variables, of which there will be seven. β_3 is a coefficient vector for the LA dummy covariates;

ε_{jk} = residual error term.

Given the large number of secondary outcomes, the secondary outcome tests for YP will be corrected for multiple comparisons using Hochberg's step-up procedure⁹. Likewise, but independently, the tests for the four secondary outcomes for FCs will be corrected.

Subgroup analyses

The trial is relatively small, with an expected sample size of under 210 per arm with complete baseline and follow-up data on the primary outcome. There are no prior expectations of large differential impacts across sub-groups of YP, and the sample size is too small for modest differences across groups to be identified. For these reasons, very little sub-group analysis is planned. The exception is that the primary YP outcome will be presented split by ethnic group (generated by running separate regression models per sub-group) to facilitate future meta-analysis, but excluding any ethnic groups with less than 30 YP per arm.

For the secondary social worker outcome, ARTIC, a joint YPSW/SSW analysis will be undertaken but, subject to some evidence of impact, separate models will be run and presented for YPSWs and SSWs.

Further analyses of the primary trial data

Sensitivity of the effect sizes to changes in YP and FC social workers during the trial

This is a pragmatic trial and it is not possible for the evaluation team to influence the allocation of YPSWs to YPs or the allocation of SSWs to FC, or, of course, the matching of YPs to FCs. An issue that will inevitably arise during the trial relates to the fact that the intervention is being delivered to social workers rather than to the YP themselves. Because YP may change their YPSW, and their FCs may change their SSW, between baseline and follow-up, a control group YP could, during the trial, be re-assigned to a YPSW or SSW who has been trained, and an intervention group YP could be re-assigned to a YPSW or SSW who has not been offered the training¹⁰. These post-randomisation switches are likely to dampen the ITT effect sizes. To test the sensitivity of the ITT estimates to these issues, we will re-run the main

⁹ This is the approach recommended by the What Works for Children's Social Care.

¹⁰ Similarly a YP could move to a new FC with a SSW from the opposite arm of the trial.

two-group analyses per outcome after excluding these switched cases¹¹. Given that the switching is likely to be largely independent of the random allocation – it is more likely to be done by the LA teams for very practical reasons – this should still give close to unbiased estimates, albeit for what may be a non-random subset of YP. However, prior to running this analysis, we will test the assumption that the switching is independent of the random allocation, using a t-test for proportions.

Imbalance at baseline and follow-up

The trial report will summarise baseline characteristics for the two primary arms of the trial for all YP for whom we have baseline data, and separately, for those with both valid baseline and follow-up data. The differences at baseline will provide evidence on whether missing data at baseline (because of baseline non-response by FCs) introduced an imbalance across the arms; the differences at follow-up will provide evidence on whether attrition post-baseline has introduced an imbalance. Note, we do not expect there to be any major imbalances at baseline associated with FC non-response, because the decision taken by a FC on whether or not to take part should be independent of the randomisation. In most cases the baseline data was collected prior to randomisation, but where it was collected post-randomisation, the FC would have been very unlikely to be aware of the allocation of their SSW or their foster child's YPSW.

The characteristics shown will be: YP randomised per LA, gender, age, ethnic group, SDQ externalising mean at baseline, and SDQ internalising and prosocial score means at baseline.

Missing data

We will describe and summarise the extent of missing data per outcome, and the reasons for data being missing where known will be reported on. We will document how much missing data is unit non-response and how much is item non-response, and whether there is evidence for trial imbalance because of missing data either at baseline or follow-up.

The primary ITT regression analysis will be based on complete cases, that is those for which all of the variables needed for the model are complete. The implicit assumption here is that missing data at follow-up is 'missing completely at random' (MCAR). However, because the rate of missing data in this trial is inevitably high (because of non-response to the surveys by FCs either at baseline or follow-up), we will assess the sensitivity of the results to alternative assumptions about the mechanisms leading to missing data.

¹¹ We ruled out analysis that tries to control for these switches because we will not have rich enough data to know when during the trial period the switch occurred, and because of the additional complexity introduced because both or just one of the professionals could be switched

Firstly, we will use the baseline outcome variables for YP and FCs¹², together with other YP and FC characteristics to model (via a logistic regression) the probability per YP of a case being in the intervention arm rather than the control arm. This will identify any observable predictors of imbalance, and the regression model (Eq 1) will be re-run to include, as covariates, any significant predictors that are identified from this logistic regression. This will help establish whether the effect sizes are influenced by the level and nature of missing data, under an assumption of missing at random (MAR).

Secondly, we will make use of the fact that the SSDA903 data will provide total SDQ scores at baseline and follow-up for many of the young people in the trial, the main exceptions being those young people who have been looked-after continuously for less than 12 months and those aged 17¹³. We will test whether there is evidence of non-response bias in the trial by comparing the mean SSDA903 scores for respondents and non-respondents at each time point, separately within each arm of the trial. If there are observed differences in the means this will allow for an estimate of the magnitude and direction of any bias.

Finally, if there is evidence that outcomes data is missing not at random (MNAR) we will include some estimates of effect sizes based on a range of extreme assumptions about the missing outcomes. This will generate upper and lower bounds for the effect sizes. The assumptions adopted for this sensitivity analysis will include imputing the worst possible outcomes scores for those missing from the intervention arm and the best possible outcomes scores for those missing from the control arm.

The approach will be repeated across all of the secondary outcomes with the probable exception of the SSDA903 outcomes, where we do not anticipate much missing data.

Compliance

Defining 'compliance' for YP in the trial is not straightforward because of the fact that the intervention is being delivered to social workers rather than to the YP themselves, so YP 'compliance' is dependent on the decisions of their YPSWs and SSWs. Because YP may change their YPSW, and their FCs may change their SSW, between baseline and follow-up, compliance

¹² FC baseline data will be used in the model because it is FCs who complete the data about YP.

¹³ The SDQ scores from the SSDA903 will not be affected by attrition so the sample sizes will be larger and non-response bias less likely. However, it is being used as an outcome measure in its own right for a range of reasons. The SDQ recorded in the SSDA903 excludes YP who are over 16 and only includes YP who have been looked-after continuously for at least 12 months. Also, the timing of the data collection can vary during the year, so the data is not at a fixed outcome point. Experience on other studies (in particular the evaluation of the Mockingbird programme) has been that SDQ data is often missing from SSDA903 submissions which would reduce its usefulness. However, early indications on the current trial are that it is close to complete.

is not a binary variable per YP per social worker. Furthermore, a control group YP could, during the trial, be re-assigned to a YPSW or SSW who is in the intervention arm (and vice versa), further complicating the definition of compliance.

Compliance with the training for social workers will be defined as a binary variable. The definition of compliance to be used is attendance of 4 out of 7 training sessions plus 2 out of 3 reflective practice sessions. In light of this, we will define compliance for YP in the intervention group as that one or both of their YPSW and SSW at baseline are compliant with the training.

The problem of YP being re-assigned to a social worker from the opposite arm of the trial is likely to be unrelated to the trial itself, so it seems reasonable to assume it will affect both of the primary analysis arms of the trial equally. In light of this, we will run a CACE analysis to isolate the impact of compliance with the training after excluding these switched-arm cases from the data.

We will re-run the ITT primary outcome regression model to generate the ITT effect size for this reduced dataset. Complier Average Causal Effect (CACE) will then be used to estimate the effect size for the 'social worker compliers' (as defined above). This will be estimated using two stage least squares (2SLS) regression. The first stage will model the compliance variable using the same explanatory variables used for the headline ITT analyses. This will be a multilevel logistic regression model used to generate predicted compliance for use in the second stage model. The second stage models will use predicted compliance in place of the group identifier variable in the ITT analyses specified above to generate the CACE estimate.

A separate CACE analysis will be conducted for the secondary social worker outcome, ARTIC.

Intra-cluster correlations (ICCs)

The trial is clustered within YPSWs. For the YP primary and secondary outcomes, ICCs will be presented, calculated at pre and post-test as the between-cluster variance divided by the total variance from the regression models. In addition, for the post-test, the ICC using the variance components from the adjusted regression model will be presented.

Presentation of outcomes

Effect sizes will be calculated using Hedges' g , as specified in the following equation:

$$ES = \frac{(\underline{Y}_T - \underline{Y}_C)_{adjusted}}{s}$$

where \underline{Y}_T is the regression adjusted mean for the treatment group, \underline{Y}_C is the regression adjusted mean for the control group (computed using Eq 1), and s^2 is the pooled unconditional variance of the two groups (derived from the raw data).

Effect sizes will be reported along with confidence intervals and p-values to reflect statistical uncertainty.

Analysis of all four arms of the trial

An exploratory analysis for the primary and secondary outcomes will include Analysis Arms 3 and 4 in the regression model, that is the groups of YP where one social worker (YPSW or SSW) was randomised to training and the other to control. For this analysis the trial will be assumed to follow a factorial design. The regressions for this analysis will generate three effect estimates: the effect of the intervention being delivered to SSWs; the effect of the intervention being delivered to YPSWs; and the additive effect of the intervention being delivered jointly to SSWs and YPSWs (that is, the interaction effect). Differences between the effect sizes will be tested for significance, but given the relatively small sample sizes in Arms 3 and 4 we do not anticipate they will reach significance, so the results will be presented purely descriptively. Given that Arms 3 and 4 are not balanced with Arms 1 and 2 (see randomisation section), this analysis will be presented with suitable caveats, and the fact that the effect sizes may be biased, will be explained.

The model for this analysis is:

$$Y_{ijk} = \beta_0 + \beta_1 Z_{1ik} + \beta_2 Z_{2ik} + \beta_3 Z_{1ik} Z_{2ik} + \beta_4 X_{ijk} + \beta_5 LA_k + u_{ijk} + \varepsilon_{ijk} \quad (\text{Eq 4})$$

where

Y_{ijk} = outcome score at follow-up for young person i assigned at baseline to YPSW j within LA k;

$\beta_0, \beta_1, \beta_2, \beta_3, \beta_4, \beta_5$ = fixed effect parameters;

Z_{1ik} = indicator variable for allocation of the YP's YPSW (0=control; 1=intervention) within LA k;

Z_{2ik} = indicator variable for allocation of the YP's SSW (0=control; 1=intervention) within LA k;

X_{ijk} = baseline externalising score for young person i assigned at baseline to YPSW j within LA k;

LA_k = a vector for the local authority dummy variables, of which there will be seven. β_3 is a coefficient vector for the LA dummy covariates;

u_{ij} = random effect for ith member of YPSW j;

ε_{ijk} = residual error term for ith member of cluster j.

